### Description of any new methods and why an improvement

Currently there are no neuromodulation therapies available to address sexual arousal. Our approach of translating an approach validated for other pelvic organs represents a new direction in this field. Furthermore, these periodic clinic stimulation sessions, if efficacious, may lead to novel non-regular sessions that reduce the load on patients or potentially to small minimalist implants that provide more user control. Either of these approaches would represent a novel approach in the field.

## Recruitment & Retention Plan

### Population characteristics

The proposal involves a 30-subject prospective study of surface electrode stimulation (dorsal genital nerve or posterior tibial nerve) weekly sessions for improving sexual arousal. As described below, adult women over the age of 18 who are neurologically stable and have intercourse at least once a month will be candidates. Typical patients will likely be in excess of 40 years of age. During each stimulation session, subjects will be reclined in a chair or examination table and will have electrodes placed at the appropriate location. After setting of parameters, stimulation will be applied for 30 minutes in duration.

We will be recruiting patients primarily from [name] pelvic pain clinic as described below. The characteristics of the patients include dyspareunia (pain with intercourse), and/or pelvic or bladder pain. The bulk of [name] pain in this clinic (~5 new patients each session, plus similar numbers of return visits) have pain with intercourse and pelvic pain as major components of their complaints. There is a sexual health therapist present in the clinic who sees most of the new patients, so we will have a psychosocial evaluation for many of them.

Patients will also be recruited from the OB/GYN clinic, other sex therapists' clinics, and UHS.

### Sampling plan

We will seek patients who meet the study inclusion and exclusion criteria. Due to the relative short timeframe of this study length, we will not perform any random sampling of potentially eligible patients and will approach each candidate on a first come first serve system. There are no ethnic distributions of targeted/planned enrollment.

### Inclusion criteria

- Adult women  $\geq 18$  years of age
- Sexually active  $\geq 1$  time per month ( $\geq 2$  times per month preferred)
- Having sexual dysfunction as identified by a score of 19 or less on the FSFI-6 [16].

For each question: Over the past four weeks...						
How would you rate your level (degree) of sexual desire?		Very high (5)	High (4)	Moderate (3)	Low (2)	Very low or none at all (1)
How would you rate your level of sexual arousal ("turn on") during sexual activity or intercourse?	No sexual activity (0)	Very high (5)	High (4)	Moderate (3)	Low (2)	Very low or none at all (1)
How often did you become lubricated ("wet") during sexual activity or intercourse?	No sexual activity (0)	Almost always or always (5)	Most times (4)	Sometimes (3)	A few times (2)	Almost never or never (1)
When you had sexual stimulation or intercourse, how often did you reach orgasm?	No sexual activity (0)	Almost always or always (5)	Most times (4)	Sometimes (3)	A few times (2)	Almost never or never (1)

How satisfied have you been with your overall sexual life?	Very satisfied (5)	Mod-erately satisfied (4)	About equally satisfied and dissatisfied (3)	Mod-erately dissatisfied (2)	Very dissatisfied (1)	
How often did you experience discomfort or pain during vaginal penetration?	Did not attempt intercourse (0)	Almost never or never (5)	A few times (4)	Some-times (3)	Most times (2)	Almost always or always (1)

- Neurologically stable
- Ambulatory
- Capable of giving informed consent
- English speaking
- Capable and willing to follow study procedures

### Exclusion criteria

- Pregnant or planning to get pregnant during the study period
- Clinically diagnosed neurological bladder dysfunction
- Prior experience with PTNS or DGNS
- Use of TENS on pelvis, back or legs
- Implanted pacemaker, defibrillator, spinal cord stimulator, or sacral root stimulator
- Vaginal infection
- Coagulation disorders
- Taking any investigational drug

### Recruitment and retention

Potential subjects will be recruited from an investigator’s clinic or related clinics. Only inclusion/exclusion criteria that are provided by the patient as part of their check-in procedures or prior visits will be used to make a decision to approach a potential study subject. If a patient expresses interest in the study, then eligibility based on the full inclusion/exclusion criteria list will be verified.

The study coordinator/nurse will follow up with the patient to schedule the stimulation sessions and will administer the baseline surveys (American Urological Association Symptom Index - AUA, Female Sexual Function Index – FSFI, Short Form Health Survey – SF-36) via mail or email. Informed consent will be obtained in person at the first stimulation session, prior to any intervention. After each session, the coordinator will remind subjects of subsequent meetings.

Patient personal information will be protected per HIPAA guidelines.

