### Collection, analysis and interpretation of results

Each study subject will be assigned an identification number. Only this number will be used to identify subjects in any individual tabulation. It is expected that only group data will be published. If individual subject data is to be published, no identifying information will be included. The study files will be maintained in a secure location. Access to computerized data will be restricted to IRB-approved study personnel. Password authorization will be enforced.

The study coordinator or other research team staff will provide both the FSFI and the SF-36 surveys to each subject, in paper form, upon their initiation into the study. Subjects will be given up to an hour to complete the survey by circling their responses on the paper form. The form for each subject will have the identification number as the only identifying piece of information on it. This same sequence will be performed at the other data collection points – after 6 weeks of testing (in the clinic before the 7th stimulation session) and after the 12th session. For the 6-week post-trial follow-up, a research staff will contact each subject to complete the survey over the phone, or will allow the subject to complete the survey and mail back in if they will not be visiting the clinic during that time.

As described in the appendices, each survey has a scoring method that yields a total quality of life score and a total sexual satisfaction score. These scores will be compared across the different time points as discussed above. The study team will meet with a statistical consultant (UM Center for Statistical Consulting and Research) to confirm correct approaches and conclusions. The study team will also compare the results found to other reported studies in the literature that used similar methods and analysis approaches for consistency. As described in the appendices, each survey has sub-sections that we may compare individually, if the data suggests any sub-section trends.

Data collection will be limited to the investigators and the research staff. All study personnel who have access to the data will be educated regarding the need to protect confidentiality and the procedure to be followed to ensure such protection. All staff will also be required to sign a standard medical record confidentiality agreement.

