### Plan for recruitment, informed consent process

Eligible subjects will be identified through the treating physicians, and will be recruited in clinic by a study coordinator or team member. [name] has a pain clinic on the 1st, 3rd, and 5th Tuesday afternoon of each month at the Von Voigtlander clinic that is called the Female Pelvic and Urinary Pain clinic. [name] runs this clinic with [name] from Urology. In addition, [name] and his partners have general urogynecology clinics at which subjects could be recruited.

Prior to the initiation of the study, an IRB approval for the study of human subjects will be obtained. The consent form will include all of the elements required by the FDA and state, local, and institutional regulations. Comprehensive written consent will be obtained from subjects prior to participation. A study coordinator or investigator will approach subjects to obtain informed consent.

Open, witnessed and non-coercive discussion will be undertaken prior to signing of the consent document.

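### Two sections give incompatible procedures for the baseline surveys; one of them, if followed, would place the surveys before consent and on a different route from weeks 6 and 12

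*Combined protocol and SAP*

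**What the plan says.** Four sections of the combined protocol and SAP bear on the baseline surveys.

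- **Recruitment and retention.** The coordinator or nurse "will follow up with the patient to schedule the stimulation sessions and will administer the baseline surveys", named as the AUA index, the FSFI and the "SF-36) via mail or email". The section then states: "Informed consent will be obtained in person at the first stimulation session, prior to any intervention". It gives no date by which the surveys must be returned.
- **Plan for recruitment, informed consent process.** "Comprehensive written consent will be obtained from subjects prior to participation".
- **Collection, analysis and interpretation of results.** Staff will "provide both the FSFI and the SF-36 surveys to each subject, in paper form, upon their initiation into the study", and "Subjects will be given up to an hour to complete the survey by circling their responses on the paper form". Then: "This same sequence will be performed at the other data collection points", namely week 6, in the clinic before session 7, and week 12, after session 12. For the follow-up six weeks later, "a research staff will contact each subject to complete the survey over the phone", or the woman mails the form back if she is not coming to the clinic.
- **Description of methods and analysis.** Four surveys (FSFI, SF-36, AUA, PGIC) are taken before study initiation, at 6 and 12 weeks, and at the long-term point. FSFI and SF-36 are compared among these time points within each stimulation group separately, by a two-sided rank sum test at 0.05. There is no control stimulation.

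**The concern.** Staff cannot follow both baseline procedures, and nothing says which one governs. Two consequences follow if the mail or email route is used.

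The first is the order of consent. Surveys sent out at scheduling would naturally be answered before the first session, and so before the consent taken there. They include intimate questions on sexual function.

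The second is comparability. With no control stimulation, each group's baseline is its only untreated reference. If baseline is completed remotely and weeks 6 and 12 under a staff-provided, time-limited paper procedure, any effect of that difference on how women answer is mixed with the change attributed to stimulation. The plan discloses that it has no control. The difference in survey route is an additional one, undisclosed and avoidable.

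**Working it through.** There is no figure in the plan to reproduce: the sample size (2 × 15 = 30) rests on precedent and feasibility, without an effect size. The check is a comparison of texts, a count, and an illustration on assumed values.

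**1. The baseline procedures side by side**

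| | Recruitment and retention | Collection, analysis and interpretation |
|---|---|---|
| Route | mail or email | paper, provided by staff |
| When | when sessions are scheduled | at initiation into the study |
| Time limit | none stated | one hour |
| Surveys | AUA, FSFI, SF-36 (3) | FSFI, SF-36 (2) |
| Same as weeks 6 and 12? | no | yes, by its own wording |

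Description of methods and analysis gives a third list, of four surveys. A mailed form may be paper, so the certain difference is remote against staff-provided completion; by email the medium may differ as well.

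**2. Order of consent.** A baseline survey must precede the first stimulation, and consent is taken at that same visit. A survey mailed or emailed beforehand is therefore most naturally completed before consent. This agrees with the rule on written consent before participation only if completing a survey is not participation, and the documents do not say so.

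**3. Comparisons affected.** Pairs among four time points: 4 × 3 / 2 = 6. Times 2 surveys (FSFI, SF-36) and 2 groups: 6 × 2 × 2 = 24. Baseline–6 and baseline–12 weeks: 2 × 2 × 2 = 8. All 8 cross a change of route under the mail or email baseline; none do under the paper baseline.

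Counting the long-term survey too, with 4 comparisons per pair of time points:

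| Long-term survey done | Remote baseline | Paper baseline |
|---|---|---|
| in clinic | 3 pairs × 4 = 12 | 0 |
| mailed back | 4 pairs × 4 = 16 | 3 pairs × 4 = 12 |
| by phone | 5 pairs × 4 = 20 | 3 pairs × 4 = 12 |

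**4. Illustration of size (assumed values).** The documents give no size for a route effect. Assume normal scores for 15 women at both times, no stimulation effect, within-woman correlation ρ, and a shift of s SD due to route alone: follow-up = ρ × baseline + √(1 − ρ²) × noise + s. Exact two-sided rank sum test at 0.05, 40,000 runs per cell; percent with p < 0.05:

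| ρ | s = 0 | 0.2 | 0.3 | 0.5 |
|---|---|---|---|---|
| 0.3 | 2.03 | 4.42 | 7.84 | 20.33 |
| 0.5 | 0.85 | 2.61 | 5.21 | 17.62 |
| 0.7 | 0.14 | 1.03 | 2.75 | 14.20 |

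The rates start below 5% because the rank sum test ignores the pairing. A paired signed-rank test under the same assumptions (20,000 runs, ρ = 0.5 and 0.7) gives about 5% at no shift, 11–15% at 0.2 SD, 18–28% at 0.3 SD and 42–62% at 0.5 SD.

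**The case against.** The strongest reply is that this is an inconsistency in documentation and not a demonstrated bias. Much of that stands.

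- A reader might infer that the baseline does differ in setting from weeks 6 and 12. The documents do not establish this: it holds only if the mail or email instruction is followed. The clinic is written as the place of completion only for week 6; for baseline and week 12 it is inferred from the staff-provided, timed procedure.
- A reader might infer that the plan knowingly collects data without consent. It does not say so. No return date is given, one section puts consent before intervention and another before participation, and participation is not defined.
- The illustration is noticeable only for large assumed shifts. At 0.2 SD the planned test stays below its nominal 5%. The 8 comparisons share baselines, so they are not independent chances of a false signal. The plan introduces the rank sum test for comparing subject groups; its use within a group is the natural reading but is not spelled out, and a paired test would be more sensitive to a shift.
- With no control stimulation, within-group change cannot be attributed to stimulation whichever route is used. Harmonising the surveys removes one contributor only.

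None of this resolves the two incompatible instructions or the order of consent, and neither depends on the size of a route effect.

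**Conclusion.** The concern holds as a conflict in the current text. The mail or email baseline and the staff-provided paper baseline are incompatible, and the former would, on its natural reading, precede consent. That contradicts the separate consent requirement if completing surveys counts as participation.

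For the analysis, the consequence is conditional: 8 of 24 within-group comparisons cross a change of route under one instruction and none under the other. The size and direction of any effect are unknown. On the assumptions shown, a shift of 0.2 SD or less changes little under the planned test (1.0–4.4%), while 0.5 SD would give 14.2–20.3%. The latter is not an estimate of what will happen.

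A reader might also infer that the DGNS-versus-PTNS contrast is biased. The documents do not support that: both groups share the survey schedule, so a common route effect would not systematically favour either.

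This should be changed, but it does not invalidate the trial.

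**What to change.** Reconcile Description of methods and analysis, Collection, analysis and interpretation of results, Recruitment and retention, and Plan for recruitment, informed consent process, so that:

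1. written consent is taken before any survey is completed;
2. one stated list of baseline surveys (now four, two or three, depending on the section) is then self-completed on paper, under the staff-provided procedure, before the first stimulation;
3. weeks 6 and 12 use the same form and setting, with one stated timing relative to the session, since week 6 is now before a session and week 12 after one;
4. the actual mode and date of every survey are recorded, including the long-term one.

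The cost is protocol wording, up to an hour more at the first visit, and two recorded fields at each of four time points: 2 × 4 = 8 per woman, 8 × 30 = 240 in all.

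The fix does not reach the long-term survey. If that is done by phone or mailed back, up to 12 comparisons still cross a change of setting. Four of these (baseline to long-term) would not do so with a mailed baseline and a mailed-back follow-up. Recording the mode makes this visible but does not remove it.

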### Plan for recruitment, informed consent process

Eligible subjects will be identified through the treating physicians, and will be recruited in clinic by a study coordinator or team member. [name] has a pain clinic on the 1st, 3rd, and 5th Tuesday afternoon of each month at the Von Voigtlander clinic that is called the Female Pelvic and Urinary Pain clinic. [name] runs this clinic with [name] from Urology. In addition, [name] and his partners have general urogynecology clinics at which subjects could be recruited.

Prior to the initiation of the study, an IRB approval for the study of human subjects will be obtained. The consent form will include all of the elements required by the FDA and state, local, and institutional regulations. Comprehensive written consent will be obtained from subjects prior to participation. A study coordinator or investigator will approach subjects to obtain informed consent.

Open, witnessed and non-coercive discussion will be undertaken prior to signing of the consent document.

